10.2 Definitions

Adverse Event:

An adverse event (AE) is any untoward or unfavorable medical occurrence in a human subject, including abnormal sign, symptom or disease, temporally associated with the subject's participation in research, whether or not considered related to the subject's participation in the

research. Abnormal results of diagnostic procedures are considered to be adverse events if the abnormality:

- results in study withdrawal
- is associated with a serious adverse event
- is associated with clinical signs or symptoms
- leads to additional treatment or to further diagnostic tests
- is considered by the investigator to be of clinical significance

Serious Adverse Event:

Adverse events are classified as serious or non-serious. A serious adverse event is any AE that is:

- fatal
- life-threatening
- requires inpatient hospitalization/prolongation of existing hospitalization, unless:
 - routine treatment or monitoring of the studied indication, not associated with any deterioration in condition (procedures such as central line placements, paracentesis, pain control)
 - elective or pre-planned treatment for a pre-existing condition that is unrelated to the indication under study and has not worsened since the start of study drug
 - treatment on an emergency outpatient basis for an event not fulfilling any of the definitions of an SAE given above/below and not resulting in hospital admissions
 - social reasons and respite care in the absence of any deterioration in the patient's general condition
- results in persistent or significant disability or incapacity
- a congenital anomaly or birth defect
- an important medical event

Important medical events are those that may not be immediately life threatening, but are clearly of major clinical significance. They may jeopardize the subject, and may require intervention to prevent one of the other serious outcomes noted above. For example, drug overdose or abuse, a seizure that did not result in in-patient hospitalization or intensive treatment of bronchospasm in an emergency department would typically be considered serious.

All adverse events that do not meet any of the criteria for serious events should be regarded as non-serious adverse events.

Unanticipated Problem:

An unanticipated problem is any incident, experience or outcome involving risks to subjects or others in any human subjects research that meets all of the following criteria:

- Unexpected (in terms of nature, severity or frequency) given (a) the research procedures that are described in the IRB-approval protocol and informed consent document, and (b) the characteristics of the subject population being studied;
- Related or possibly related to participation in such research (e.g., there is a reasonable possibility that the incident, experience or outcome may have been caused by the procedures involved in such research); and

- Suggests that the research places subjects or others at a greater risk of harm (including physical, psychological, economic or social harm) than was previously known or recognized.

Adverse Event Reporting Period

The study period during which adverse events must be reported is normally defined as the period from the initiation of any study procedures (e.g., after the first dose of study treatment) to the end of the study treatment (e.g., last dose of study treatment) and/or follow-up. For this study, the study treatment follow-up is defined as 30 days following the last administration of study treatment, **or 30 days following the decision to remove the subject from study treatment, whichever is earliest.**

Baseline/Preexisting Condition

A baseline/preexisting condition is one that is present at the start of the study. A preexisting condition should be recorded as an adverse event if the frequency, intensity, or if the character of the condition worsens during the study period.

General Physical Examination Findings

At screening, any clinically significant abnormality should be recorded as a preexisting condition. At the end of the study, any new clinically significant findings/abnormalities that meet the definition of an adverse event must also be recorded and documented as an adverse event.

Post-study Adverse Event

All unresolved adverse events should be followed by the investigator until the events are resolved, the subject is lost to follow-up, or the adverse event is otherwise explained. At the last scheduled visit, the investigator should instruct each subject to report any subsequent event(s) that the subject, or the subject's personal physician, believes might reasonably be related to participation in this study.

Abnormal Laboratory Values

A clinical laboratory abnormality should be documented as an adverse event if any one of the following conditions is met:

- The laboratory abnormality is not otherwise refuted by a repeat test to confirm the abnormality
- The abnormality suggests a disease and/or organ toxicity
- The abnormality is of a degree that requires active management (e.g., change of dose, discontinuation of the drug, more frequent follow-up assessments, further diagnostic investigation, etc.).

Hospitalization, Prolonged Hospitalization or Surgery

Any adverse event that results in hospitalization or prolonged hospitalization should be documented and reported as a serious adverse event unless specifically instructed otherwise in this protocol. Any condition responsible for surgery should be documented as an adverse event if the condition meets the criteria for an adverse event.

Neither the condition, hospitalization, prolonged hospitalization, nor surgery are reported as an adverse event in the following circumstances:

- Hospitalization or prolonged hospitalization for diagnostic or elective surgical procedures for a preexisting condition. Surgery should **not** be reported as an outcome of an adverse event if the purpose of the surgery was elective or diagnostic and the outcome was uneventful.
- Hospitalization or prolonged hospitalization required to allow efficacy measurement for the study.
- Hospitalization or prolonged hospitalization for therapy of the target disease of the study, unless it is a worsening or increase in frequency of hospital admissions as judged by the clinical investigator.

10.3 Recording of Adverse Events

At each contact with the subject, the investigator must seek information on adverse events by specific questioning and, as appropriate, by examination. Information on all adverse events should be recorded immediately in the source document, and also in the appropriate adverse event module of the case report form (CRF). All clearly related signs, symptoms, and abnormal diagnostic procedures results should be recorded in the source document, though should be grouped under one diagnosis.

All adverse events occurring during the study period must be recorded. The clinical course of each event should be followed until resolution, stabilization, or until it has been determined that the study treatment or participation is not the cause. Serious adverse events that are still ongoing at the end of the study period must be followed up to determine the final outcome. Any serious adverse event that occurs after the study period and is considered to be possibly related to the study treatment or study participation should be recorded and reported immediately.

Reporting of Serious Adverse Events

10.4.1 IRB Notification by Sponsor-Investigator

Reports of all events (including follow-up information) that meet the definition of an unanticipated problem posing risk to subjects or others must be submitted to the IRB within one week (5 business days) following the occurrence of the unanticipated problem or the principal investigator's acquiring knowledge of the unanticipated problem in accordance with IRB policy. Additionally, the sponsor-investigator will submit a summary of all Unanticipated problems that occurred since the beginning of the study at the time of continuing review. Copies of each report and documentation of IRB notification and receipt will be kept in the Regulatory binder.

10.4.2 FDA Notification by Sponsor-Investigator

The Columbia University Medical Center Sponsor-Investigator, as holder of the IND, will be responsible for all communication with the FDA. Columbia University Medical Center Sponsor-Investigator will report to the FDA, regardless of the site of occurrence, any adverse event that is serious, unexpected and there is evidence to suggest a causal relationship between the drug and the adverse event. These must be reported to the FDA and any affiliate sites as soon as possible, but in no case later than 15 calendar days after the sponsor determines that the information qualifies for reporting. The Sponsor-Investigator will also submit an IND annual report to the

FDA in accordance with 21.CFR 312.33.

The Columbia University Medical Center Sponsor Investigator must report to the FDA and any affiliate site investigators as follows:

- Any unexpected fatal or life-threatening event must be reported as soon as possible, but no later than 7 calendar days after the sponsor investigator initial receipt of the information
- Any findings from epidemiological studies, pooled analysis of multiple studies, or clinical studies, whether or not conducted under an IND, and whether or not conducted by the sponsor-investigator, that suggest a significant risk in humans exposed to the drug must be reported as soon as possible but no later than 15 calendar days after the sponsor-investigator determines that the information qualifies for reporting
- Any findings from animal or in vitro testing whether or not conducted under an IND, and whether or not conducted by the sponsor-investigator, that suggest a significant risk in humans exposed to the drug must be reported as soon as possible but no later than 15 calendar days after the sponsor-investigator determines that the information qualifies for reporting
- Any clinically important increase in the rate of a serious suspected adverse reactions over that listed in the protocol or Investigator Brochure
- Expected SAEs and AEs will be included in the IND Annual Reports.

Follow-up information to a safety report should be submitted as soon as the relevant information is available. However, if the results of a sponsor's investigation show that an adverse drug experience not initially determined to be reportable are so reportable, the sponsor investigator must report such experience as soon as possible, but no later than 15 calendar days after the determination is made.

All other serious unexpected experiences associated with the use of the study treatment will be reported to FDA as soon as possible but in no event later than 15 calendar days after initial receipt of the information.

10.4.3 DSMC Reporting by the Sponsor Investigator

Serious adverse events not constituting unanticipated problems are to be reported to the HICCC DSMC. Reporting should occur within 24 hours of knowledge of the SAE occurring at our institution or affiliate sites.

Participating investigators must report each serious adverse event to the Columbia University Medical Center Overall Principal Investigator within 24 hours of learning of the occurrence using the SAE Report Form. In the event that the participating investigator does not become aware of the serious adverse event **immediately** (e.g., participant sought treatment elsewhere), the participating investigator is to report the event within 24 hours after learning of it and document the time of his or her first awareness of the adverse event. Report serious adverse events by telephone, email or facsimile to:

[name]

[name]
[name]
[contact]
[contact]
Email address: [contact]

Within the following 24-48 hours, the participating investigator must provide follow-up information on the serious adverse event. Follow-up information should describe whether the event has resolved or continues, if and how the event was treated, and whether the participant will continue or discontinue study participation.

10.4.4 Reporting to Drug Manufacturer by Sponsor-Investigator

SAE Reporting to Incyte

The Sponsor-Investigator must report all Serious Adverse Events (SAEs) to Incyte within 24 hours of learning of an event, regardless of the PIs causality assessment. This notification should be provided on a completed Serious Adverse Event (SAE) form. SAE reporting for each subject begins the day the informed consent is signed by the patient and within 30 days after subject has completed or discontinued from the study or has taken last dose of the study drug, or as described in the protocol.

SAEs, occurring using Incyte Study drug, are reported in accordance with the effective protocol. SAEs occurring with any other commercial drug are reported to the manufacturer of that drug in accordance with regulations and protocol.

Initial SAEs and/or subsequent follow-up reports should be reported via email to [contact] or fax [name]. SAE reports should be for a single subject. SAE forms should be sent with a cover sheet and any additional attachments.

All adverse event information is reported to Incyte on the Principal Investigator's/Institution's Adverse Event Report Form, or a CIOMS-I or MedWatch Form FDA 3500A, or on an Adverse Event Report Form which may be provided by Incyte upon request. The Principal Investigator does not provide medical records (e.g., discharge summary) to Incyte, unless specifically requested.

Reporting of Pregnancy to Incyte

An "Initial Pregnancy Report" or equivalent must be completed in full and emailed to [contact] or faxed to [name] within 24 hours of discovery of a pregnancy of a subject who has taken the Incyte product or the pregnancy of a partner for a subject who has taken the Incyte product. The "Follow-up Pregnancy Report Form" or equivalent must be completed and emailed to [contact] or faxed to [name] within 30 days after delivery, so that Incyte is provided with information regarding the outcome of the pregnancy. If the pregnancy results in any events which meet the serious criteria (i.e., miscarriage or termination), the SAE reporting process needs to be followed and the timelines associated with a SAE should be followed.

The Sponsor-Investigator will report to investigational agent manufacturer any serious adverse events that meet the reporting criteria to the Institutional Review Board as described in section 10.4 and/or to the FDA as described in section 10.4 within 24 hours of becoming aware of it, so that these reports can be evaluated and included in the Investigator's Brochure and for IND safety submissions per regulations. Reporting will occur by sending the reporting form along with any additional documentation sent to the regulatory authorities.

At the time of IRB renewal or at the request of the manufacturer, the Sponsor-Investigator will submit a summary of all Serious Adverse Events that have occurred inclusive of all sites to manufacturer.

10.4 Reporting Process

Adverse events may be submitted on FDA Form 3500A, the HICCC DSMC Serious Adverse Event Reporting Form, or in a narrative format. If supplied as in a narrative format, the minimum information to be supplied is noted above at the beginning of section 10.

11. PHARMACEUTICAL INFORMATION

11.1 Description

Ruxolitinib phosphate is a kinase inhibitor with the chemical name (R)-3-(4-(7H-pyrrolo[2,3-d]pyrimidin-4-yl)-1H-pyrazol-1-yl)-3-cyclopentylpropanenitrile phosphate and a molecular weight of 404.36.

Ruxolitinib phosphate is a white to off-white to light pink powder and is soluble in aqueous buffers across a pH range of 1 to 8. Ruxolitinib tablets are for oral administration. Each tablet contains ruxolitinib phosphate equivalent to 5 mg, 10 mg, 15 mg, 20 mg and 25 mg of ruxolitinib free base together with microcrystalline cellulose, lactose monohydrate, magnesium stearate, colloidal silicon dioxide, sodium starch glycolate, povidone and hydroxypropyl cellulose.

11.2 Treatment Regimen

Ruxolitinib is an orally-administered tablet. Patients with adequate hematologic counts will be started on a dose of 10mg twice daily. Dosing will be adjusted for safety as delineated. Treatment will consist of 28-day cycles. Treatment will continue until disease progression or severe toxicity requiring cessation.

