| Diagnosis and Main Inclusion Criteria | 
Main Inclusion Criteria:
 
 • Histopathologically confirmed diagnosis of metastatic advanced cutaneous squamous cell carcinoma. • History of solid-organ transplant requiring immunosuppression • Age ≥ 18 yrs • Measurable disease by RECIST v1.1 • KPS $\geq 60\%$, ECOG ≤ 2 • No prior JAK Inhibitor therapy • Adequate organ function • All clinically significant toxicities from prior systemic therapy must be \leq Grade 1 (with the exception of alopecia, and peripheral neuropathy, which may be \leq grade 2). • Subjects must agree to undergo tumor biopsies until biopsies have been obtained from 10 subjects (i.e., biopsies are required in at least the first 10 enrolled subjects, or until a goal of 10 study biopsies are obtained). Subjects in whom a biopsy is technically not feasible or in whom would result in unacceptable risk in the opinion of the investigator, may be exempted from the biopsy requirement with discussion with the principal investigator. • Negative pregnancy test for women of child bearing potential • Ability to take oral medications • Adequate marrow function: 
 - ANC ≥ 1000 /mm³ - Platelet count $\geq 50,000$/mm³ - Hemoglobin ≥ 8.0g/dL (not requiring transfusion in the past 2 weeks) |
| Study Product, Dose, Route, Regimen | Ruxolitinib will be administered orally twice daily during the entirety of each 28-day cycle. There will be a safety lead-in cohort of 6 patients who receive the starting dose of 15mg twice daily (BID). If dose limiting toxicities (DLT) are seen in 1 or fewer patients, the starting dose for all remaining patients will be 15mg BID. If DLT's are seen in >1 patient, another 6 patients will be enrolled at 10mg BID. If DLT's are seen in 1 or fewer patients, the starting dose for the remaining patients will be 10mg BID. Otherwise the study will be terminated. Individual subjects may have dose reductions of ruxolitinib during the course of treatment, based upon safety laboratory assessments. |

| | |
|-----------------------------------|---|
| Duration of administration | Treatment with ruxolitinib will commence following enrollment and continue until objective disease progression as confirmed by RECIST v1.1, intolerable toxicity or the occurrence of another discontinuation criterion. |

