5. STUDY DESIGN

5.1 General Design

This is an open-label, multi-center, Phase II study to evaluate the efficacy of ruxolitinib in post-transplant patients with advanced cutaneous squamous cell carcinoma.

Study Intervention: In a safety lead-in of 6 patients, subjects will receive ruxolitinib 15mg BID. After 4 weeks, if dose-limiting toxicities (DLT) are observed in 1 or fewer patients, the study will enter stage 1 of the Simon two-stage design where all subsequent patients will receive a starting dose of ruxolitinib 15mg BID. If more than 1 DLTs are observed, another cohort of 6 patients will be treated at a dose of 10mg BID. If less than 2 DLTs are observed at the new dose of 10mg, then the study will proceed to stage I using this dose; otherwise the study will stop.

Individual subjects may have dose reductions of ruxolitinib during the course of treatment, based upon safety laboratory assessments.

Schedule of Evaluations: Subjects will have regularly scheduled study visits at the clinical site on Day 1 and Day 15 (\pm 3 days) of the first cycle, then on Day 1 (\pm 3 days) of every subsequent cycle (starting cycle 2), where safety assessments, including laboratory assessments, vital signs, and physical examinations will be performed (see Section 12 for study calendar).

Response to treatment will be determined by CT scans of the chest, abdomen, and pelvis with contrast. The overall response rate for the primary endpoint evaluation will be determined by RECIST v1.1 criteria. In patients who are unable to get a CT scan w/ contrast due to renal function (or any other reason), an MRI with and without contrast may be used instead. Imaging will be performed at the following time points:

| | |
|--------------------------------------|---|
| Baseline scan | Baseline scan within 4 weeks prior to first treatment |
| Weeks 1 – 32 | Every 8 weeks +/- 1 week (at weeks 8, 16, 24, 32) |
| Weeks 33 – until disease progression | Every 12 weeks +/- 1 week (at weeks 44, 56, 68, 80, 92, 104) |
| 2 years | If subjects achieve ongoing disease control at 2 years, patients will be continued on study treatment and observed with imaging every 12 weeks +/- 2 weeks. |

Duration of treatment: Subjects will continue treatment until confirmed radiographic disease progression, intolerable toxicity or side effects (Section 6.5.1).

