8. TREATMENT PLAN

8.1 Agent Administration

Treatment will be administered on an outpatient basis. Reported adverse events and potential risks for ruxolitinib are described in Section 10. Appropriate dose modifications for ruxolitinib are described in Section 9. No investigational or commercial agents or therapies other than those described below may be administered with the intent to treat the patient's malignancy.

If all eligibility criteria are met, study participants will initiate ruxolitinib twice daily. One cycle will consist of 4 weeks of therapy.

- Patients will be provided with a Medication Diary for ruxolitinib (Appendix D), instructed in its use, and asked to bring the diary with them to each appointment.
- Doses of ruxolitinib will be taken orally with approximately 8 oz. of water. Subjects should fast at least 1 hour before administration and 1 hour after administration

of the drug. Study drug should be taken at approximately the same time each day. Study drug should be swallowed whole and not crushed, chewed, or dissolved in water.

- Missed doses (outside of a 2 hour dosing window) should be skipped and not administered as a double dose at the next administration. Missed doses should be recorded on the Medication Diary but will not be considered violations of the protocol.
- Subjects who vomit their dose should be instructed NOT to make up that dose. Doses that are vomited should not be replaced.
- Patients will be instructed that ruxolitinib can be stored at room temperature.
- No premedication or other supportive medications are required.

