8.1.1 Investigational Agent(s)

Ruxolitinib will be administered twice daily, in the morning and evening, approximately 12 hours apart, without regard to food. If a dose is late but within 4 hours of its scheduled administration time it should be taken; if more than 4 hours have passed, the dose should be omitted and the patient should continue treatment with the next scheduled dose. If vomiting occurs while taking dose, no redosing is allowed before the next rescheduled dose.

Patients will not require any premedications, however supportive medications to control symptoms such as nausea, emesis, diarrhea, and pain will be provided for symptom control.

Doses will be self-administered. Subjects will be required to keep a pill diary (Appendix D). Each cycle of treatment will last 28 days.

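### Section 11.2 starts patients at 10 mg BID, contradicting the 15 mg BID lead-in of the Synopsis and Section 5.1

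*Combined protocol and SAP*

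**What the plan says.** Section 5.1 sets the dose through a lead-in: "In a safety lead-in of 6 patients, subjects will receive ruxolitinib 15mg BID". After 4 weeks, if at most one patient has had a DLT, everyone who follows starts at 15 mg BID. Otherwise, "If more than 1 DLTs are observed, another cohort of 6 patients will be treated at a dose of 10mg BID". If that cohort has fewer than two DLTs, "then the study will proceed to stage I using this dose; otherwise the study will stop".

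The Synopsis, in its row on study product, dose, route and regimen, gives the same rule. Six patients start at 15 mg BID. Only after DLTs in more than one of them does the lower dose appear: "another 6 patients will be enrolled at 10mg BID". The remaining patients start at 10 mg BID only if at most one patient in that second cohort has a DLT.

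Section 11.2, in the pharmaceutical information chapter, says: "Patients with adequate hematologic counts will be started on a dose of 10mg twice daily". The only condition is blood counts. The section mentions neither 15 mg, nor the lead-in, nor DLTs.

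The other dosing text does not choose between them. Section 8.1 says "If all eligibility criteria are met, study participants will initiate ruxolitinib twice daily" and Section 8.1.1 says "Ruxolitinib will be administered twice daily, in the morning and evening, approximately 12 hours apart, without regard to food"; neither gives a starting dose in milligrams. Table 1 in Section 9.2 lists four dose levels without naming the start. The pill diary in Appendix D leaves the daily dose for staff to fill in.

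**The concern.** The starting dose is an operative instruction, and the protocol states it in two ways that cannot both apply to a lead-in patient. Section 11 is where a research pharmacist would naturally look for the regimen, and three centers take part, so different readers could act on different text.

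What is at stake is the lead-in. Its purpose is to show whether 15 mg BID is tolerable before the two-stage design proceeds at that dose. If the first six patients were started at 10 mg BID, their DLT count would say nothing direct about 15 mg BID.

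**Working it through.** The plan states no figure on this point that needs reproducing. The check is a comparison of every place that states or bears on the starting dose, with simple arithmetic for its size.

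**Side by side**

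| Place | Lead-in start | When 10 mg BID is used |
|---|---|---|
| Synopsis, dose row | 15 mg BID, 6 patients | Second cohort of 6, after DLTs in more than 1 patient |
| Section 5.1 | 15 mg BID, 6 patients | Second cohort of 6, after more than 1 DLT |
| Section 11.2 | Lead-in not mentioned | At the start, for patients with adequate counts |
| Sections 8.1, 8.1.1 | No milligram dose | Not stated |
| Section 9.2, Table 1 | No starting level marked | Listed as level 0 |

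**Size of the difference**

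- Synopsis and Section 5.1: 15 mg × 2 = 30 mg/day.
- Section 11.2: 10 mg × 2 = 20 mg/day.
- Relative difference: (30 − 20)/30 = 33% lower.

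**Is 10 mg BID a start or a fallback in this design?** Sections 5.2 and 17.1 plan 35 patients, with a maximum of 41 if a second lead-in is needed: 35 + 6 = 41. That fits 10 mg BID being held in reserve.

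The documents give no expected DLT rate, so the chance of reaching the fallback can be shown only over assumed rates. With true DLT probability p at 15 mg BID, the chance that at least 2 of 6 patients have a DLT is 1 − (1 − p)^6 − 6p(1 − p)^5:

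| Assumed p | (1 − p)^6 | 6p(1 − p)^5 | Chance of moving to 10 mg BID |
|---|---|---|---|
| 10% | 0.5314 | 0.3543 | 11.4% |
| 20% | 0.2621 | 0.3932 | 34.5% |
| 30% | 0.1176 | 0.3025 | 58.0% |
| 40% | 0.0467 | 0.1866 | 76.7% |

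Across this range the 10 mg BID cohort is an outcome of the lead-in, not a certainty. Section 11.2 writes it as the start without that condition.

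**Does Table 1 decide the matter?** Its levels are 15 mg BID (level 1), 10 mg BID (level 0), 5 mg BID (level −1) and 5 mg once daily (level −2). The toxicity tables take a patient off therapy after more than two reductions.

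- From 15 mg BID, two one-level reductions end at 5 mg BID.
- From 10 mg BID, two one-level reductions end at 5 mg once daily.

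Under that limit, level −2 can be reached only from a 10 mg BID start. The numbering and the lowest level therefore fit Section 11.2, but they also fit the fallback start in Section 5.1. The top level of 15 mg BID fits the Synopsis and Section 5.1. Table 1 points both ways.

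**The case against.** The strongest reply is that no careful site would be misled. The Synopsis has a row devoted to dose and regimen, Section 5.1 spells out the intervention, and they agree; one sentence in the pharmaceutical chapter should not outweigh them. Followed alone, Section 11.2 also errs toward the lower dose. This stands in part: the harm is conditional on a site acting on Section 11.2. It does not remove the contradiction, because no text says which section governs.

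One could also say that Section 11.2 goes on to allow dose adjustment for safety. That sentence concerns changes after the start and does not bring in the lead-in rule.

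A reader might infer more than the documents support, in three ways:

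- **That Table 1 proves Section 11.2 wrong.** It does not, as shown above. The case for 15 mg BID rests on two agreeing statements of the full rule and on the accrual maximum that fits it.
- **That up to 6 + 6 = 12 patients would be treated at 10 mg BID and none at 15 mg BID.** This needs Section 11.2 for the lead-in, Section 5.1 for the fallback, and more than one DLT at 10 mg BID.
- **That Stage 1 would open at a dose (30 − 20)/20 = 50% above the one observed.** This needs Section 11.2 for the lead-in and Section 5.1 afterwards.

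The last two are possible mixtures of sections; no single section prescribes either.

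**Conclusion.** The protocol is wrong as written: an internal inconsistency in the starting dose, 30 versus 20 mg/day. It should be corrected. The likely intended dose is 15 mg BID, which is a judgment from two concordant places and needs the sponsor's confirmation. If the sponsor has in fact moved to 10 mg BID, nothing in the documents says so, and the Synopsis and Section 5.1 would then be the text to amend.

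The practical effect arises only where a site or pharmacy follows Section 11.2; the documents do not allow an estimate of how many patients that would be. A reader might also suppose that the conflict disturbs the efficacy design. It does not: starting dose is not an input to the Simon boundaries, alpha or power.

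**What to change.** Subject to sponsor confirmation, replace the starting-dose sentence in Section 11.2 with:

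> The starting dose is 15 mg BID for the 6 lead-in patients. After the 4-week DLT observation, the starting dose for later patients is the one selected by the rule in Section 5.1: 15 mg BID if at most 1 of 6 has a DLT; otherwise a second cohort of 6 at 10 mg BID, continuing at 10 mg BID if at most 1 of those has a DLT, else the study stops.

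In Table 1, mark 15 mg BID as the starting level and 10 mg BID as the fallback start.

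As a separate clean-up that adds no weight to the dose point, align the Synopsis hematology limits with Section 6.1. The Synopsis has ANC 1000/mm³, platelets 50,000/mm³ and hemoglobin 8.0 g/dL without transfusion in the past 2 weeks. Section 6.1 has 1.5 × 10⁹/L, 100 × 10⁹/L and 9 g/dL with transfusion allowed. The three Synopsis values equal the cycle-start limits in Section 9.1, which may be where they came from.

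The cost is a clarifying amendment and a memo to sites and pharmacies, with no added patients or procedures.
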